### 3.1.3 Schema

Dose Level	Dose and Schedule
1 N = 3 to 6	1 site of injection at $2 \times 10^8$ IU given every 28 days for 3 doses.
2 N = 10-16	2 sites of injection at $2 \times 10^8$ IU given every 28 days for 3 doses.
3 N = 10-16	4 sites of injection at $2 \times 10^8$ IU given every 28 days for 3 doses.

Dose escalation will proceed in cohorts of 3–6 patients. The MTD is the dose level at which no more than 1 of up to 6 patients have DLT during the first 28 days of treatment, and the dose below that at which at least 2 (of  $\leq 6$ ) patients have DLT as a result of the drug. If a patient did not experience DLT and did not complete the DLT evaluation period (28 days), he or she will not be evaluable for toxicity and will be replaced in the dose level as outlined in the Statistical Design (Section 8).

Dose escalation will follow the rules outlined in the table below.

**Confidential**

*Abbreviated Title: Phase I MVA-Brachyury-TRICOM*

*Version Date: September 14, 2016*

Number of Patients with DLT at a Given Dose Level	Escalation Decision Rule
0 of 3	Enter up to 3 patients at the next dose level
$\geq 2$	Dose escalation will be stopped. This dose level will be declared the maximally administered dose (highest dose administered). Up to three (3) additional patients will be entered at the next lowest dose level if only 3 patients were treated previously at that dose.
1 of 3	Enter up to 3 more patients at this dose level. 
 
• If 0 of these 3 patients experience DLT, proceed to the next dose level.
 
• If 1 or more of this group experience DLT, then dose escalation is stopped, and this dose is declared the maximally administered dose. Up to three (3) additional patients will be entered at the next lowest dose level if only 3 patients were treated previously at that dose.
 

$\leq 1$ of 6 at highest dose level below the maximally administered dose	This is the MTD and is generally the recommended phase II dose. At least 6 patients must be entered at the recommended phase II dose.

### 3.2 DRUG ADMINISTRATION

MVA-brachyury-TRICOM is supplied frozen in single-use vials. The vial must be thawed at room temperature for approximately 10-15 minutes prior to preparation, and should not be re-frozen after thawing. The thawed suspension will appear milky and may contain clumps or aggregates. To ensure homogeneity, the vial should be swirled vigorously, but not shaken, for approximately 10 – 20 seconds immediately prior to use. The thawed drug product is to be drawn into a syringe with an appropriately sized safety shielded needle suited to patient comfort (e.g. 22- to 28-gauge). MVA-brachyury-TRICOM is to be administered via subcutaneous injection in the upper arm and/or outer thigh per the schedule described in Section 3.1.3.

### 3.3 STUDY CALENDAR

	Baseline	Day 1	Day 29	Day 57	Restaging Day 85	Day 169 and every 85 days thereafter until progression
History and	X					

**Confidential**

**Abbreviated Title: Phase I MVA-Brachyury-TRICOM****Version Date: September 14, 2016**

physical 						
Medical assessments 	X		X 	X 	X 	X
Imaging	X 				X	X
Urinalysis	X		X	X	X	X
Serum HIV antibody 	X					
Serum hepatitis B & C 	X					
CBC with differential, platelet count	X 		X	X	X	X
Chemistry 	X 		X	X	X	X
EKG	X 				X	X
Correlative / Immunology (blood) 	X		X	X	X	X
ANA titer	X				X	X
CD3, 4, 8, 19 subsets, NK markers and CD4:CD8 ratio	X		X		X	X
HLA typing	X					
Serum beta-HCG 	X					
Pulse oximetry	X					
MVA-brachyury-TRICOM vaccine 		X	X	X		
Adverse events			X	X	X	X
Concomitant medications	X		X	X	X	X

Baseline: H & P and laboratory studies should be completed within 16 days of initiating treatment. Baseline radiographic, EKG, and immunologic studies should be obtained within 28 days of initiating treatment.

Medical assessments: interim history (since last visit), vital signs, physical examination and ECOG performance status. To be performed at baseline, within 3 days of each dose of vaccine and with each restaging visit (about every 85 days on study).

Radiologic studies consisting of CT chest/abdomen/pelvis (and MRI or bone scan when appropriate for tumor type) will be performed within 28 days prior to initiating treatment, on about day 85, and about every 85 days until progression.

Serum HIV antibody should be completed within 8 weeks of initiating treatment.

Serum hepatitis B & C antibody should be completed within 8 weeks of initiating treatment.

Chemistry panel: Na+, K+, Cl, CO2, glucose, BUN, creatinine, albumin, calcium, magnesium, phosphorus, alkaline phosphatase, ALT, AST, total bilirubin, TSH, and LDH.

In females of child-bearing age, beta-HCG to be done at baseline within 48 hours prior to day 1.

Within 3 days prior to each vaccination.

Administered subcutaneously at 1, 2, or 4 sites (days 1, 29, 57 all - 4 days up to +14 days. In the event a dose is delayed, all subsequent doses will be scheduled about 28 days from that dose.)

Correlative / Immunology blood: 6 (10mL) green top sodium heparin tubes for PBMC; 2 (8mL) SST tubes for serum samples, and 2 (10mL) green top sodium heparin tubes for circulating tumor cell assay.

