## 2 ELIGIBILITY ASSESSMENT AND ENROLLMENT

### 2.1 ELIGIBILITY CRITERIA

#### 2.1.1 Inclusion Criteria (All Subjects)

- 2.1.1.1 Patients must have a metastatic or unresectable locally advanced malignant solid tumor, histologically confirmed by the Laboratory of Pathology, NCI. In the case of chordoma, unresectable, locally recurrent, or metastatic tumors are acceptable for enrollment, given that this represents incurable disease. Efforts will be made, as much as possible, to enroll patients with tumor types with known increased expression of brachyury (such as lung, breast, ovarian, prostate, colorectal, pancreatic, or chordoma; other tumors may be included as data on the level of brachyury in those tumors becomes available).
- 2.1.1.2 Patients may have measurable or nonmeasurable but evaluable disease. See Section 6.2 for the evaluation of measurable disease. Patients with surgically resected metastatic disease at high risk of relapse are also eligible.
- 2.1.1.3 Prior therapy: Patients must have completed or had disease progression on at least one prior line of disease-appropriate therapy for metastatic disease, or not be candidates for therapy of proven efficacy for their disease.
- 2.1.1.4 There should be a minimum of 4 weeks from any prior chemotherapy, immunotherapy and/or radiation, with the exception of hormonal therapy for prostate and breast

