**Confidential**

cancers, HER2-directed therapy for HER2+ breast cancer (3+ IHC or FISH+), and erlotinib in EGFR-mutated lung cancer in the expansion cohort as detailed in section. There should be a minimum of 6 weeks from any prior antibody therapies, (such as ipilimumab or anti-PD1/PDL1) due to prolonged half-life.

- 2.1.1.5 Patients must have recovered (grade 1 or baseline) from any clinically significant toxicity associated with prior therapy. Typically, this is 3–4 weeks for patients who most recently received cytotoxic therapy, except for the nitrosoureas and mitomycin C, for which 6 weeks is needed for recovery.
- 2.1.1.6 Age  $\geq$  18 years. Because no dosing or adverse event data are currently available on the use of MVA-brachyury-TRICOM vaccine in patients < 18 years of age, children are excluded from this study but will be eligible for future pediatric trials.
- 2.1.1.7 ECOG performance status  $\leq$  1 (Karnofsky  $\geq$  70%, see Appendix A, Section 13.1).
- 2.1.1.8 Patients must have normal organ and marrow function as defined below:
- Serum creatinine  $\leq$  1.5 x upper limit of normal OR creatinine clearance on a 24-h urine collection of  $\geq$  50 mL/min.
  - ALT and AST  $\leq$  3x the upper limits of normal.
  - Total bilirubin  $\leq$  1.5 x upper limit of normal OR in patients with Gilbert's syndrome, a total bilirubin  $\leq$  3.0.
  - Hematological eligibility parameters (within 16 days of starting therapy):
    - Granulocyte count  $\geq$  1,500/mm^3
    - Platelet count  $\geq$  100,000/mm^3
- 2.1.1.9 Patients must have baseline pulse oximetry > 90% on room air.
- 2.1.1.10 The effects of MVA-brachyury-TRICOM on the developing human fetus are unknown. For this reason, women of child-bearing potential and men must agree to use adequate contraception (hormonal or barrier method of birth control; abstinence) prior to study entry and for the duration of study participation and for a period of 4 months after the last vaccination therapy. Should a woman become pregnant or suspect she is pregnant while she or her partner is participating in this study, she should inform her treating physician immediately.
- 2.1.1.11 Patients with prostate cancer must continue to receive GnRH agonist therapy (unless orchiectomy has been done). If a patient has refused GnRH therapy, they may be enrolled on a dose level for which the safety has already been determined.

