  - 2.1.3.6 Concurrent use of systemic steroids, except for physiologic doses of systemic steroid replacement or local (topical, nasal, or inhaled) steroid use. Limited pharmacologic doses of systemic steroids (e.g., in patients with exacerbations of reactive airway disease or to prevent I.V. contrast allergic reaction or anaphylaxis in patients who have known contrast allergies) are allowed.
  - 2.1.3.7 Patients who are receiving any other investigational agents within 28 days before start of study treatment.
  - 2.1.3.8 Patients with untreated central nervous system metastases or local treatment of brain metastases within the last 6 months. Patients with stable brain metastasis for 6 months post-intervention are eligible. Subjects with chordoma will be eligible regardless of site of disease if other eligibility criteria are met.
  - 2.1.3.9 History of allergic reactions attributed to compounds of similar chemical or biologic composition to MVA-brachyury-TRICOM or other agents used in study.
  - 2.1.3.10 Serious or uncontrolled intercurrent illness including, but not limited to, ongoing or active infection, symptomatic congestive heart failure, unstable angina pectoris, cardiac arrhythmia, or psychiatric illness/social situations that, in the opinion of the investigator, would limit compliance with study requirements.

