Because we will be using new evaluation techniques with a first in human study, we will enroll 10 patients in an expansion cohort, resulting in 16 potential evaluable patients in the two highest tolerated dose level cohorts, which will provide 80% power to detect a change in T-cell precursors from baseline equal to 1.0 standard deviations of the difference (effect size = 1.0) using a 2-tailed 0.05 alpha level paired t-test. All 10-16 patients in each dose level with evaluable T-cell precursor data at this dose level will be included in the analysis, with 10 patients providing an illustration of 80% power based on that minimal number. The actual power could be greater than 80% if 11-16 patients are evaluable for this determination. In practice, a nonparametric Wilcoxon signed rank test will be used. A positive response using the flow based intracellular cytokine staining assay will be defined as the frequency of T lymphocytes positive for a cytokine or CD107a post-vaccine being increased greater than two-fold compared to both (1) pre-vaccine values and (2) HLA control post-vaccine; the fraction of the patients who have a positive response out of those evaluable for this determination will be noted and reported along with a corresponding 95% confidence interval.

Although the MTD will have been declared after 6 patients at that dose level have been evaluated, monitoring for toxicity in the additional cohort of patients will continue. In the event that more than one third of all patients enrolled at the MTD experience a DLT, protocol modifications will be undertaken to reduce the likely level of toxicity in future patients prior to continuing to enroll additional subjects.

Clinical response evaluation will take place in the patients enrolled at the MTD and the expansion cohort. The results will be considered secondary and will be used to determine the parameters for a subsequent phase II trial should the preliminary findings from this trial warrant further investigation.

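### The only scheduled pre-vaccine immune sample may be up to 28 days old at dose 1 and is not tied to the end of the washout, so the paired change test cannot separate earlier immune drift from vaccine effect

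*Combined protocol and SAP*

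**What the plan says.** **Timing of the immune baseline.** Section 3.3, footnote 1: "Baseline radiographic, EKG, and immunologic studies should be obtained within 28 days of initiating treatment". The same footnote gives the history, physical and laboratory studies a shorter window of 16 days. In the calendar, the Correlative/Immunology row has draws at Baseline, Day 29, Day 57, Day 85 and from Day 169 onward. The CD3/4/8/19, NK and CD4:CD8 row has Baseline, Day 29, Day 85 and later. The Day 1 cell is empty in both rows.

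**Washout.** Section 2.1.1.4: "There should be a minimum of 4 weeks from any prior chemotherapy, immunotherapy and/or radiation", with named exceptions, and "There should be a minimum of 6 weeks from any prior antibody therapies". Neither rule states the date to which the interval runs. By contrast, exclusion 2.1.3.7 is explicit: "Patients who are receiving any other investigational agents within 28 days before start of study treatment".

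**Recovery.** Section 2.1.1.5: "Patients must have recovered (grade 1 or baseline) from any clinically significant toxicity associated with prior therapy". It adds that this typically takes 3–4 weeks after cytotoxic therapy. It sets no lymphocyte or T-cell criterion.

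**Analysis.** Section 8 assesses T-cell precursors both as absolute change and as a positive response. The change is tested within patients at each dose level. Power is calculated for a paired t-test, and a Wilcoxon signed rank test is to be used in practice. A positive response by intracellular staining requires the post-vaccine frequency "being increased greater than two-fold compared to both (1) pre-vaccine values and (2) HLA control post-vaccine". There is no control arm and no adjustment for time since prior therapy.

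**The concern.** In a single-arm before-and-after design, the pre-treatment value is the only reference. It should reflect the patient's state when treatment starts. Here it may reflect a state up to four weeks earlier, in patients who may have recently stopped chemotherapy, immunotherapy or radiation. If an immune measure moves in that interval for any reason, the movement becomes part of the measured change, and no later pre-dose sample exists to reveal it.

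Detecting change in T-cell precursors is the stated reason for adding 10 patients at each of the two highest tolerated dose levels. A bias in the reference value therefore falls on the analysis that those patients are enrolled to support. More patients do not help: at a fixed drift, the chance of a false finding rises with sample size.

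**Working it through.** **1. Timing.** Day 0 below means dose 1. The earliest permitted immune baseline is day −28.

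- *4-week washout counted to dose 1.* The latest permitted prior therapy is day −28. Smallest gap from last therapy to sample: 28 − 28 = 0 days.
- *Antibody therapy, 6 weeks counted to dose 1.* Smallest gap: 42 − 28 = 14 days.
- *4-week washout complete at registration, sample drawn afterwards.* The gap is at least 28 days and there is no overlap. The sample can still be up to 28 days old at dose 1.
- *Subset panel.* Section 2.3.1 lists it under laboratory studies without its own window. If footnote 1's 16-day laboratory window applies, the smallest gap with a washout counted to dose 1 is 28 − 16 = 12 days. If it counts as an immunologic study, the gap is as in the first line.

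**2. The plan's own figure.** Section 8 states 80% power for a change of 1.0 SD of the difference, two-sided alpha 0.05, paired t-test, illustrated with 10 patients. For a paired t-test with n patients and mean change d in SDs of the difference, t has n − 1 degrees of freedom and noncentrality d√n. The test rejects when |t| exceeds the 0.975 quantile.

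- n=10, d=1.0: noncentrality 3.162, critical value 2.262, power 80.3%. The stated figure is reproduced.
- n=16, d=1.0: 96.2%.
- Wilcoxon with exact critical value, 200,000 simulated normal samples: 78.5% at n=10 and 94.9% at n=16.

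**3. The same formula with no vaccine effect.** Let d be the cohort-mean drift between the baseline draw and dose 1, persisting to the post-vaccine sample. The values of d are assumptions.

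| Mean drift (SD of difference) | n=10, any significant change | n=16, any significant change |
|---|---|---|
| 0 | 5.0% | 5.0% |
| 0.2 | 8.8% | 11.6% |
| 0.3 | 13.6% | 20.3% |
| 0.5 | 29.3% | 46.5% |

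For upward drift, nearly all of these rejections are rises. At 0.5 SD and n=10, a rise is declared in 29.28% of trials and a fall in 0.03%; with no drift the rate for a rise is 2.5%.

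Wilcoxon, the test to be used, adding rises and falls:

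- 0.25 SD: 10.3% + 0.4% = 10.6% before rounding of the parts at n=10; 13.6% + 0.2% = 13.8% at n=16. The t-test gives 10.9% and 15.5%.
- 0.5 SD: 28.2% at n=10; 42.9% at n=16.

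**4. Dilution.** These are cohort means. If one third of patients drifted by 0.5 SD and the rest not at all, the mean would be 0.5/3 ≈ 0.17 SD. Ignoring the small change in SD that such a mixture brings, the formula then gives about 8% at n=10 and 10% at n=16.

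**The case against.** Several points on the other side stand, and they limit the finding.

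- *Overlap with the last day of therapy.* A reader might infer that the baseline can always coincide with the last prior treatment. That needs the 4 weeks to run to dose 1, and 2.1.1.4 does not say so. It is an eligibility criterion, and Section 2.4 has an eligible candidate registered within 24 hours of consent, which supports a reading with no overlap. Both readings are open. Neither removes the four-week-old baseline.
- *Recovery as a known upward bias.* A reader might take the 3–4 weeks in 2.1.1.5 as the time T cells need to recover. That text concerns clinical toxicity. The main readout is a frequency among T lymphocytes, and recovery of cell numbers need not raise an antigen-specific proportion. No section gives the size or direction of drift.
- *The responder rule.* A reader might conclude that the two-fold rule fails in the same way. Its second condition compares with a control measured after vaccination, so a non-specific rise would tend to raise both and not qualify. This protection is partial: recovery of existing brachyury-specific cells could still meet both conditions. The absolute-change, subset and cytokine readouts have no such guard.
- *Who is affected.* Expansion patients who continue erlotinib, hormonal, HER2-directed or maintenance therapy have no washout from that drug, and others may be long past treatment. This reduces the mean drift, as step 4 shows.

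The objection does not supply a rule that ties the sample to dose 1, a second pre-dose sample, or an analysis that allows for time since prior therapy.

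**Conclusion.** The concern holds in a limited form. The immune baseline is not anchored to dose 1 or to the end of the washout, and Section 8's paired comparison counts everything that happens after that draw as change from baseline. Non-vaccine drift before dose 1 therefore cannot be told apart from vaccine effect.

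The size is unknown. The rates of 9% to 29% at n=10 and 12% to 46% at n=16 are illustrations under assumed mean drifts of 0.2 to 0.5 SD and no vaccine effect. They are not estimates for this trial, and they would be lower if few patients come straight from therapy.

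The documents do not support a claim that the immune results will be inflated, or that safety conclusions are at risk. Secondary objectives 1.1.2.1 and 1.1.2.3 are affected. The primary safety objective and the dose-escalation decisions, which rest on dose-limiting toxicity, are not. The change is worth making because it is cheap and removes an avoidable ambiguity from the analysis that motivates the expansion cohorts.

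**What to change.** In Section 3.3, remove immunologic studies from the 28-day window in footnote 1. Schedule the baseline Correlative/Immunology and CD3/4/8/19/NK samples on Day 1 before vaccination, or within 3 days before, the interval footnote 8 already uses. Align Section 2.3.1 so that the subset panel has one stated window. In Section 8, define this sample as the pre-vaccine value. Imaging and ECG can keep their 28 days.

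If the 4-week washout is counted to dose 1, a Day 1 draw falls at least 28 days after the last washed-out therapy, and a draw 3 days earlier at least 28 − 3 = 25 days after. If it is counted to registration, the gap is no shorter. The ambiguity in 2.1.1.4 then matters little for this analysis.

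Cost: a calendar and footnote edit, with matching lines in Sections 2.3.1 and 8. Tubes and number of draws are unchanged, the patient already attends on Day 1, and the planned power is unaffected (80.3% at n=10). The downside is that a failed Day 1 sample cannot be repeated once vaccine is given; the 3-day option leaves some room for a repeat.

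The change removes drift before dose 1. It does not remove recovery that continues after dose 1, which a single-arm design cannot separate from vaccine effect, and the report should say so.

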### **3 STUDY IMPLEMENTATION**

#### **3.1 STUDY DESIGN**

This is an open-label phase I trial with sequential cohorts of patients (3–6 patients per dose cohort to establish safety) with dose escalation of MVA-brachyury-TRICOM vaccine (see Section 8). Three cohorts will receive MVA-brachyury-TRICOM vaccine administered subcutaneously as either 1, 2, or 4 injections of study drug (1 injection =  $2 \times 10^8$  IU) at monthly (28 days– 4 days up to +14 days) intervals for 3 months (treatment). A dose will be considered missed if not given within 14 days of the original schedule and the patient will resume treatment with the next scheduled dose. The time of patient monitoring post injection would be 2 hour observation after first dose and 30 minutes after subsequent doses.

Toxicity in the 28 days following the first vaccination after the 3rd subject (or 6th subject, if applicable) in dose levels 1 through 3 will be employed for decision-making (i.e., for dose-escalation and for maximum tolerable dose estimation). Inpatient dose escalation will not be allowed. In addition, patients may be enrolled as an expansion cohort at the MTD and at the dose level just below the MTD after either 0 of 3 or no more than 1 of 6 patients have been treated at that dose level and have not experienced a DLT for at least 28 days. Cohorts 2 and 3 will accrue up to an additional 10 evaluable patients each (up to 16 patients total in each) for safety and correlative analysis.

Patients will be sequentially enrolled and monitored for safety as described at dose level 2 and dose level 3. If 0 of 3 or no more than 1 of 6 patients treated at each dose level have experienced a DLT for at least 28 days, we will enroll patients on the expansion phases.

Patients may be concurrently enrolled in the expansion cohort of dose level 2 while enrolling patients on dose level 3 for safety evaluation. Any patient who is eligible will be prioritized into a dose escalation slot. Once all dose escalation slots are filled, patients will be enrolled sequentially onto the expansion phase 2, followed by phase 3. Expansion slots will only be filled by subjects who are not eligible (due to concurrent therapy) for escalation slots until safety is established in both dose level 2 and 3. There will not be randomization.

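### Pregnancy is tested only before the first vaccination; doses 2 and 3 have no scheduled beta-HCG, although fetal effects are unknown and a positive test stops vaccine

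*Combined protocol and SAP*

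**What the plan says.** **Dosing.** The Schema (3.1.3) has each dose level "given every 28 days for 3 doses". The calendar (3.3) marks vaccine at Days 1, 29 and 57. Section 3.1 allows a window of minus "4 days up to +14 days) intervals for 3 months (treatment"), and adds: "A dose will be considered missed if not given within 14 days of the original schedule". Calendar footnote 9 re-times later doses after a delay: "In the event a dose is delayed, all subsequent doses will be scheduled about 28 days from that dose".

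**Pregnancy testing.** The serum beta-HCG row of the calendar has one mark, in the baseline column. Footnote 7 reads: "In females of child-bearing age, beta-HCG to be done at baseline within 48 hours prior to day 1". Section 2.2.2 lists beta-HCG among the screening laboratory tests, with a repeat in the 48 hours before treatment, and defines who counts as a female of child-bearing potential.

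**Other checks at Days 29 and 57.** The chemistry panel in footnote 6 ends with "alkaline phosphatase, ALT, AST, total bilirubin, TSH, and LDH" and contains no HCG. The medical assessment in footnote 2 consists of "interim history (since last visit), vital signs, physical examination and ECOG performance status". Footnote 8 times it: "Within 3 days prior to each vaccination".

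**Pregnancy rules.** Section 2.1.1.10 states that fetal effects are unknown, requires contraception until 4 months after the last vaccination, and asks a woman to tell her physician at once if she is or may be pregnant. Section 2.1.3.11 excludes pregnant women because of the unknown fetal effects. Section 3.4.1 lists a positive pregnancy test as a reason to stop vaccine, and 7.3.1.1 requires treatment to stop immediately if pregnancy occurs.

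**The concern.** For dose 1 the plan wants a result no more than 48 hours old. Fetal risk is just as unknown at doses 2 and 3, yet the requirement is not carried forward and no reason is given.

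The stopping rules in 3.4.1 and 7.3.1.1 are conditional, so they do not contradict the calendar. After dose 1, however, they can take effect only if someone already suspects pregnancy or it is clinically evident. If contraception fails and the history and examination before the next dose reveal nothing, an early pregnancy is exposed to a further dose of a first-in-human product that a routine assay could have prevented.

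What is at stake is patient and fetal safety. The trial's statistical properties are not involved.

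**Working it through.** The plan gives no figure to reproduce. The check sets the scheduled tests against the scheduled doses, then counts how old the last scheduled result is at each later dose.

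**Step 1: tests against doses**

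| Day | Vaccine | Beta-HCG scheduled | Other scheduled checks that include HCG |
|---|---|---|---|
| 1 | Yes | Yes, 0–2 days before (footnote 7) | – |
| 29 | Yes | No | None |
| 57 | Yes | No | None |

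Doses without a scheduled test, per affected woman: 3 − 1 = 2 of 3. Scheduled tests between dose 1 and dose 3: 0.

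**Step 2: inputs for the day count**

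- Day 1 is taken as the day of the actual first vaccination.
- The last scheduled test is 0–2 days before it (footnote 7).
- Interval: 28 days (3.1.3). Window: −4 to +14 days (3.1 and footnote 9).
- Age of result at a dose = (dose day − 1) + (0 to 2).

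**Step 3: dose 2**

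- Nominal: 29 − 1 = 28, so 28 to 28 + 2 = **28–30 days**.
- Across the window: earliest 28 − 4 = 24; latest 28 + 14 = 42, plus 2 = 44. Range **24–44 days**.

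**Step 4: dose 3**

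- Nominal: 57 − 1 = 56, so 56 to 56 + 2 = **56–58 days**.
- Across the window, the answer depends on how the window is read:
  - *Counted from the original Day 57* (the missed-dose sentence in 3.1): Days 53 to 71. Earliest 53 − 1 = 52; latest 71 − 1 = 70, plus 2 = 72. Range **52–72 days**.
  - *Applied to each interval, with re-timing after a delay* (3.1 window with footnote 9): earliest 24 + 24 = 48 (Day 49); latest 42 + 42 = 84 (Day 85), plus 2 = 86. Range **48–86 days**, so at most about 12 weeks.

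**Step 5: the narrower window in the Précis**

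The Précis gives ±4 days. Applied to each interval:

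- Dose 2: 28 − 4 = 24 to 28 + 4 + 2 = 34, so 24–34 days.
- Dose 3: 24 + 24 = 48 to 32 + 32 + 2 = 66, so 48–66 days.

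This lowers the upper limits but leaves the nominal ages unchanged.

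**What cannot be computed.** The documents do not say how many participants will be women of child-bearing potential, so no number of affected women or doses is given.

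**The case against.** **The screening section could mean every treatment.** Section 2.2.2 asks for a repeat within 48 hours before treatment and does not say first treatment. Taken alone, that could cover each dose, and the removal criterion in 3.4.1 would fit. The reading is weak: the sentence sits in the screening list, and footnote 7 and the single baseline mark tie the test to Day 1. If testing before each dose was intended, the calendar does not say so, and the same edit cures it.

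**The existing protections are layered.** Contraception is mandatory, even a suspected pregnancy must be reported at once, and a history and examination take place within 3 days before each vaccination, when an unscheduled test can be ordered. Harm requires contraception to fail, the patient not to suspect it, and the assessment to miss it, all within a three-dose course. This stands, and it makes the event probably rare. It does not cover the early unrecognised pregnancy, which is the case an assay detects.

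**The weight is modest.** The trial enrols at most 38 patients, men included; the yield of extra tests cannot be quantified; and no rule in the documents demands a test before each dose. These points are fair and are why this is put as an improvement and not as an error. They do not outweigh a serious and possibly irreversible harm that is avoidable at very low cost.

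**The 12-week figure is an extreme.** It needs both later doses to be 14 days late with the window re-anchored. That is correct; the nominal 4 and 8 weeks are the figures to rely on.

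**Conclusion.** The concern holds. No part of the protocol schedules a pregnancy test before dose 2 or dose 3, so 2 of the 3 planned doses per affected woman rest on the pre-Day 1 result, about 4 weeks old at dose 2 and about 8 weeks old at dose 3 on the nominal schedule.

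This rests on two assumptions: that Day 1 is the actual first vaccination, and that the 2.2.2 repeat test is the one footnote 7 describes. Only females of child-bearing potential as defined in 2.2.2 are affected. The sponsor should make the change, but as a safety improvement: the plan does not contradict itself, and the DLT rule, power and analyses are untouched.

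**What to change.** 1. Add a mark in the serum beta-HCG row of the calendar at Day 29 and Day 57.
2. Replace footnote 7 with: *In females of child-bearing potential, a negative beta-HCG is required within 48 hours before each vaccination; repeat the test if the dose is postponed beyond that window.*
3. If 48 hours is impractical for doses 2 and 3, use the 3-day window that footnote 8 already sets for the medical assessment.
4. Run the assay on blood already drawn for Days 29 and 57 where the timing allows; otherwise take a separate sample.

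**Cost.** One calendar and footnote amendment, and usually two extra routine assays per affected woman, with a repeat if a dose slips after testing. The drawbacks are a short wait for the result before dosing and an occasional extra blood draw.
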